**Table 1: International Working Group Response Criteria for Hematologic Improvement**

Hematologic improvement*	Response criteria (responses must last at least 8 weeks)
Erythroid response (pretreatment a , Hgb < 11 g/dL)	1. Hgb increase by $\geq 1.5$ g/dL OR 2. Relevant reduction of units of red blood cell (RBC) transfusions by an absolute number of at least 4 RBC transfusions/8 weeks compared with the pretreatment transfusion number in the previous 8 weeks. Only RBC transfusions given for a Hgb of $\leq 9.0$ g/dL pretreatment will count in the RBC transfusion response evaluation
Platelet response (pretreatment a , Platelet < $100 \times 10^9/L$ )	1. Absolute increase of $\geq 30 \times 10^9/L$ for patients starting with $> 20 \times 10^9/L$ platelets; OR 2. Increase from $< 20 \times 10^9/L$ to $> 20 \times 10^9/L$ and by at least 100%
Neutrophil response (pretreatment a , Neutrophil absolute < $1.0 \times 10^9/L$ )	At least 100% increase and an absolute increase $> 0.5 \times 10^9/L$
Progression or relapse after HI*	At least 1 of the following: At least 50% decrement from maximum response levels in granulocytes or platelets Reduction in Hgb by $\geq 1.5$ g/dL Transfusion dependence

a Pretreatment counts averages of at least 2 measurements (not influenced by transfusions)  $\geq 1$  week apart.

b In the absence of another explanation, such as acute infection, repeated courses of chemotherapy, gastrointestinal bleeding, hemolysis, and so forth. It is recommended that the 2 kinds of erythroid and platelet responses be reported overall as well as by the individual response pattern.

Adapted from: Cheson BD, Greenberg PL, Bennett JM, et al. Clinical application and proposal for modification of the International Working Group (IWG) response criteria in myelodysplasia. *Blood*. 2006;108:419-425.

**Marrow Complete Response:** is defined as an answer of “Marrow Complete Remission” for the question “Response Assessment” in CRF form of “Response Assessment”.

**Objective Response Rate:** is defined as the proportion of subjects with PR+CR/Marrow CR . Subjects who cannot be assessed for response will be counted as non-responders.

**Pre-existing AE or Baseline AE:** is defined as in [Appendix 5](#).

**Progression-Free Survival:** PFS is defined as the time from first dose of study medication to first documentation of disease progression/relapse, or to death due to any cause, whichever occurs first. For subjects without disease progression/relapse or death on study, PFS will be censored at the time of the last on-study disease assessment demonstrating a lack of disease progression/relapse. If more than one date of progression is available, the earliest date will be used to determine PFS. Subjects who receive another antineoplastic therapy in the absence of documented progression will be censored at the time of receiving off-protocol therapy for

malignancy, EXCEPT that subjects who receive stem cell transplant in remission will continue to be followed for progression.

**Relative Dose Intensity (RDI):** is defined as the absolute dose intensity over the intended dose intensity,

$$\text{RDI} = \text{ADI} / \text{IDI} * 100.$$

Where IDI (intended dose intensity) is defined as the intended dose of drug (mg/kg) per unit of time.

**Study Drug:** The study drug is vadastuximab talirine (SGN-CD33A) for the study.

**Serious AE (SAE):** is defined as an answer of “Yes” for the question “Was this Serious” in CRF form of “Adverse Events and Pre-Existing Conditions”.

**Time Since Initial Diagnosis:** is defined as

Date of first dose – date of initial MDS diagnosis + 1.

**Transformation to AML:** is defined as an answer of “Yes” for the question “Has the patient progressed to AML” in CRF form of “Follow-Up”.

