Subjects will be stratified by baseline ECOG performance score (0 vs 1 or 2) and IPSS risk category (Intermediate-2 vs High risk).

Sample Size Considerations

Phase 1 Portion (minimum of 6 subjects per cohort): Six subjects are adequate to appropriately assess the safety profiles and DLT rates of differing dose levels of vadastuximab talirine in combination with azacitidine. If the true incidence rate of DLT is 10%, the probability of considering a dose level tolerable (ie, ≤ 1 of 6 subjects experiences a DLT) will be 88.6%. If the true incidence rate of DLT is 50%, the probability of considering a dose level tolerable will be 10.9%.

Phase 2 Portion (106 subjects): A sample size of 106 subjects will provide 85% power to detect a treatment difference in ORR, assuming an ORR of 30% for azacitidine alone vs 55% for the combination of vadastuximab talirine with azacitidine, at a 2-sided 0.1 alpha level.

Analysis Methods

The primary efficacy endpoint of the study is ORR in the Phase 2 Portion, defined as the proportion of subjects who achieve any category of CR (CR and Marrow CR) or PR based on the 2006 IWG criteria for MDS. Subjects who receive other MDS therapies before a response has been observed will be considered non-responders. The ORR will be summarized by treatment group and the corresponding 90% confidence intervals will be calculated. The treatment difference in ORR will be tested using a Cochran-Mantel-Haenszel test.

Secondary efficacy endpoints include CR rate, HI rate, DOR, PFS, rate of transformation to AML, and OS. Treatment differences in the rate of CR, HI, and transformation to AML will be analyzed by the same method as for ORR. DOR, PFS, and OS will be estimated with the Kaplan-Meier method and tested with the stratified log-rank test.

The primary analysis of efficacy will be based on the intent-to-treat (ITT) analysis set, which includes all subjects who are randomized in the Phase 2 Portion of the study.

Descriptive summaries of subject disposition, demographics, disease characteristics, baseline and pharmacodynamics biomarkers, extent of exposure to study treatment, and safety will be provided. The relationship of vadastuximab talirine PK and relevant pharmacodynamic endpoints, safety, or efficacy may be explored; these analyses, if conducted, will be descriptive.

DATE AND VERSION: 13 April 2017, Version 03

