### 9.5.2 Secondary Efficacy Endpoints

The following analyses for the secondary endpoints will be performed for the Safety set for the Phase 1 Portion and ITT and EE set for the Phase 2 Portion of the study, respectively.

CR Rate, HI rate, and Rate of transformation to AML will be summarized descriptively by treatment arm or dose level. The corresponding 90% confidence intervals for the difference in rate between the 2 treatment arms will be provided for the 2 Portion of the study.

The number and percent of subjects with disease response of CR, Marrow CR, PR, stable disease [SD], PD or Relapse from CR / PR as collected on the Response Assessment CRF form will be presented at each visit by treatment arm or dose level.

Time-to-event variables (DOR, PFS, and OS) will be summarized descriptively using the Kaplan-Meier methodology using the SAS LIFETEST procedure. Medians and quartiles and their two sided 90% CI using the complementary log-log transformation method will be calculated, where possible. PFS probability at 3, 6, 9, ...51 months with corresponding CIs will be reported. . Kaplan-Meier figures will be presented by treatment arm or dose level.

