### 9.5.4 Methods for Handling Dropouts and Missing Data

With the exception of time-related endpoints, missing observations will generally be treated as missing at random and will not be imputed, unless otherwise noted.

For time-related endpoints, DOR and PFS will follow [Table 2](#) below:

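### AML transformation is taken from one Follow-Up form question and compared as a simple proportion, so it can miss on-treatment events and makes no allowance for unequal follow-up

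*SAP*

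**What the plan says.** Protocol 8.2 and SAP 2.0 both list a between-arm comparison of the rate of transformation to AML as a secondary objective of Phase 2.

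- **Definition.** In SAP 5.0 the event "is defined as an answer of “Yes” for the question “Has the patient progressed to AML” in CRF form of “Follow-Up". The endpoint thus rests on one form question, "Has the patient progressed to AML". The entry gives no event date, time window or second source.
- **Analysis in the protocol.** The synopsis states: "Treatment differences in the rate of CR, HI, and transformation to AML will be analyzed by the same method as for ORR". For ORR that method is a Cochran-Mantel-Haenszel test on proportions. Protocol 13.6.4.2 says only that the rate will also be summarised.
- **Analysis in the SAP.** Section 9.5.2 states: "CR Rate, HI rate, and Rate of transformation to AML will be summarized descriptively by treatment arm or dose level". It adds: "The corresponding 90% confidence intervals for the difference in rate between the 2 treatment arms will be provided".
- **Time-to-event rules.** SAP 9.5.2 limits these to three endpoints: "Time-to-event variables (DOR, PFS, and OS) will be summarized descriptively using the Kaplan-Meier methodology". The rules in SAP Table 2 are equally limited: "For time-related endpoints, DOR and PFS will follow" that table. AML transformation is in neither list.
- **Missing data.** Outside the time-related endpoints, SAP 9.5.4 says that "missing observations will generally be treated as missing at random and will not be imputed, unless otherwise noted". Nothing is noted for AML.

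**The concern.** Whether a subject is seen to transform depends on how long and by what route the subject is observed, and on whether death comes first. A yes/no answer on one form, compared as a proportion, ignores all three.

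The form comes late. Long-term follow-up starts after the end-of-treatment visit, which is 30 to 37 days after the last dose (Protocol 10.3). A transformation seen in an on-treatment marrow counts only if a later Follow-Up form repeats it. If completion of that form, or length of observation, differs by arm, the difference in proportions moves with no difference in AML. The result could then be read as the combination lowering or raising AML risk when it reflects observation or mortality.

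**Working it through.** The documents give no rate, power or precision for AML transformation, so there is no figure of the plan's own to reproduce. The first step below compares provisions. The other three are illustrations on declared assumptions.

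**1. Capture, from the documents alone**

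- On-treatment marrows are examined in even-numbered cycles until CR, then every 4 cycles (Protocol Table 4), and recorded on the eCRF (Protocol 11.3). Protocol Appendix 18.6 includes, for subjects at 10%-20% blasts, a rise to above 20% as progression. The trial's own assessments can therefore document the event on treatment.
- Subjects who withdraw are not contacted again (Protocol 9.4.3.2).
- After end of treatment, scheduled marrows stop at progression, relapse, new therapy or 24 months (Protocol 11.3). Later contacts are described as collecting survival and subsequent therapy (Protocol 10.4). AML status is not named.
- For deaths, SAP 5.0 uses three CRF pages: End of Study, AE and follow-up. For AML it uses one.

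**2. Size of a capture difference (assumed)**

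Take a true 25% in each arm, with 90% of events captured in control and 70% in the experimental arm.

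- Observed rates: 0.25 × 0.90 = 22.5% and 0.25 × 0.70 = 17.5%.
- With 53 per arm (106 randomised 1:1), an unstratified two-sided z-test at 0.10, evaluated by exact binomial enumeration, finds a lower experimental rate 16% of the time. With equal capture the figure is 5%.

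**3. Size of a follow-up difference (assumed)**

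Use constant cause-specific hazards: λ for AML, μ for death without AML. The proportion seen to transform by time T is

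λ/(λ+μ) × (1 − exp(−(λ+μ)T)).

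- AML risk of 30% at 24 months in the absence of death: λ = −ln(0.7)/24 = 0.01486 per month.
- Death: median 22.5 months, the midpoint of the 21 to 24 months in Protocol 7.3, so μ = ln 2/22.5 = 0.03081 per month.
- T = 24: 0.3254 × (1 − exp(−1.096)) = 21.7%.
- T = 12: 0.3254 × (1 − exp(−0.548)) = 13.7%.

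The two arms have identical hazards, yet the rates differ by 8 points. The same test declares the arm followed for 12 months lower 28% of the time, or 22% to 34% for assumed AML risks of 20% to 40%.

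**4. What unequal death does (assumed)**

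Use the same formula per year at T = 2 with equal, complete follow-up. The control death hazard is ln 2/1.875 = 0.37. The AML hazard is the same in both arms.

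| Death hazard (per year) | AML hazard 0.15 | AML hazard 0.25 |
|---|---|---|
| 0.185 (halved) | 21.9% | 33.4% |
| 0.37 (control) | 18.7% | 28.7% |
| 0.74 (doubled) | 14.0% | 21.8% |

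For example, 0.15/0.52 × (1 − exp(−1.04)) = 18.7%. Each entry is itself the cumulative incidence of AML with death as a competing event. The table therefore shows a shift in a correctly estimated quantity. Only the cause-specific hazard ratio, which is 1 by construction, shows that AML risk among those alive and AML-free is unchanged.

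**The case against.** **Unequal death is not bias here.** A reader might infer from the table in step 4 that early deaths bias the AML rate. They do not under complete, equal follow-up: the crude proportion then equals the cumulative incidence, and the recommended estimate would show the same numbers. What remains is interpretation, because the crude difference cannot say whether AML or mortality changed. This stands, and it is why cumulative incidence alone would not be a sufficient remedy.

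**Follow-up should be roughly balanced.** Arms are randomised concurrently 1:1, blinded until the ORR analysis, and contacted every 2 months until death or study closure. The 24 versus 12 months in step 3 has no basis in the documents and is a stress case. Even so, the marrow schedule after treatment is anchored to end of treatment, which treatment can change, and withdrawal ends contact. The plan has no rule for either.

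**The subject without a form.** It is tempting to say that such subjects count as not transformed. No section says so. The non-responder rule covers response only, and SAP 9.5.4 leaves missing observations unimputed. The denominator is simply unstated.

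**Loss through death is not certain.** The follow-up page also asks whether the patient is alive (SAP 5.0), so it may be completed at death. Protocol 9.4.3.1 keeps subjects who discontinue treatment under follow-up for survival and disease status unless they withdraw. This reduces the loss. It does not help those who withdraw, or those who die without the form being completed.

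**Data availability.** The CRF is not among the documents, which show only a yes/no question. SAP 1.1 reports that hematologic improvement could not be calculated because its components were not captured. It cannot be assumed that a dated AML analysis needs no further data.

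**Conclusion.** The concern holds for the definition and for the analysis. Counting AML transformation from one undated form answer omits events documented on treatment when the subject withdraws or dies before that form is completed. A difference in proportions with no common window and no censoring is biased if follow-up differs by arm. Reading rate as a simple proportion is an inference, but a firm one: the protocol applies the ORR method, the SAP gives an interval for a difference in rate, and AML is absent from the time-to-event list.

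The documents do not fix the size. The illustrations give shifts of about 5 points for the assumed capture gap, 5 to 10 points for 24 versus 12 months of follow-up, and 5 to 7 points for a doubled death hazard. The last is a matter of interpretation, not bias. All rest on assumed AML and death hazards. Using an overall survival median for death without AML probably overstates that hazard.

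A reader might take this as a threat to the trial's main result. It is not: AML transformation is one of six secondary efficacy endpoints, the SAP summarises it descriptively, and the ORR conclusion does not depend on it. The point is a cheap improvement.

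**What to change.** - **SAP 5.0.** Define transformation to AML from any source already collected: marrow blasts at response assessments and end of treatment, AE records, and the Follow-Up form. Use the earliest qualifying date and state the blast threshold.
- **SAP 5.0 or 9.5.4.** State the denominator and how a subject with no Follow-Up form is handled.
- **SAP 9.5.2.** Report cumulative incidence of AML by arm from randomisation, with death without AML as a competing event and censoring at the last assessment of AML status. Add a stratified cause-specific log-rank test or hazard ratio, using the randomisation strata, to separate the AML effect from mortality.
- **Before database lock.** Check whether the Follow-Up form records a transformation date. If not, use the form or assessment date and say so.

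The cost is a few lines of SAP text and modest extra programming with standard software. The main risk is that some post-treatment transformations have only an approximate date.

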### **Treatment Arm, Actual**

In the Phase 1 portion, the actual treatment arm will be the dose level of vadastuximab talirine the subject received in Cycle 1, regardless of the cohort in which they were enrolled.

In Phase 2 portion of the study, a subject’s actual treatment arm (azacitidine in combination with vadastuximab talirine or azacitidine in combination with placebo) will be determined by whether the subject is administered vadastuximab talirine or placebo by merging the Treatment-Blinded Study Drug CRF data and the Medication Packs List using the Medication ID Number and the Kit Number. If a subject receives one or more dose of vadastuximab talirine, then the subject’s actual treatment arm will be azacitidine in combination with vadastuximab talirine. If a subject receives only placebo, then the subject’s actual treatment arm will be azacitidine in combination with placebo.

### **Treatment Arm, Randomized**

In Phase 2 portion of the study, a subject’s randomized treatment arm (azacitidine in combination with vadastuximab talirine or azacitidine in combination with placebo) will be the treatment arm associated with that subject’s randomization number in the IXRS randomization schedule.

**Treatment-Emergent AE (TEAE):** All AEs reported after initiation of treatment and pre-existing conditions that worsen after initiation of treatment will be considered treatment-emergent AEs (TEAEs). See [Appendix 4](#) and [Appendix 5](#) for imputation of partial AE dates and detailed pre-existing AE rules, respectively. Unless otherwise specified, summaries of AEs will only include treatment-emergent events.

**Treatment-Related-AE:** is defined as an answer of “Yes” for the question “Was this related to Vadastuximab Talirine or Blinded Study Drug” in CRF form of “Adverse Events and Pre-Existing Conditions”.

**30-day Mortality Rate:** is defined as the proportion of patients who die within 30 days from start of study therapy for Phase 1 and within 30 days from randomization for Phase 2.

**60-day Mortality Rate:** is defined as the proportion of patients who die within 60 days from start of study therapy for Phase 1 and within 60 days from randomization for Phase 2.

## 6.0 Analysis Sets

### 6.1 Intent-to-Treat Set

The intent-to-treat (ITT) set will include all subjects who are randomized in the Phase 2 Portion of the study. This set will be used for baseline and efficacy analyses. If the randomized treatment arm differs from the actual treatment at any drug administered periods for a given subject, that subject will be analyzed according to the randomized treatment arm.

### 6.2 Safety Set

The safety set will include all subjects who are enrolled and received at least 1 dose of study treatment (vadastuximab talirine, placebo or azacitidine) in both portions of the study. In the Phase 2 portion of the study, if the randomized treatment arm differs from the actual treatment, the subject will be analyzed according to the actual treatment arm. See [Section 5](#) definitions of actual and randomized treatment arm.

### 6.3 DLT-Evaluable Set

The DLT-evaluable set will include all phase 1 subjects who completed at least Cycle 1 of treatment (Cycle 1 of treatment is completed when the patient receives the first dose of azacitidine on Day 1 of Cycle 2) or discontinued study treatment because of AEs or for a safety-related reason before having had the opportunity to receive the first dose of azacitidine on Day 1 of Cycle 2, or who had a DLT. Subjects in the DLT-evaluable set will be grouped by actual dose level.

### 6.4 Modified Intent-to-Treat Set

The modified intent-to-treat (mITT) set will include all ITT subjects who received at least 1 dose of study medication (azacitidine, vadastuximab talirine, or placebo) in the Phase 2 Portion of the study. Subjects will be grouped according to their randomized treatment group assignment regardless of the treatment they actually received.

## 7.0 Interim Analyses

No formal interim analyses for efficacy are planned for this study.

### 7.1 Safety Monitoring Committee

During the Phase 1 Portion of the study, the SMC will monitor the trial for safety and dose limiting toxicities (DLTs). Each dose cohort will be evaluated for DLTs prior to enrolling the subsequent cohort. Sufficient trends in safety or toxicity identified by the SMC may result in

enrollment suspension or study termination, as recommended by the SMC. The SMC may also recommend predetermined or intermediate dose levels for dose escalation and/or expansion for the Phase 2 portion of the study based on review of safety and efficacy data. In the event of a death or emergence of a life-threatening acute or chronic toxicity within the safety reporting period, enrollment to the study will be temporarily halted until the SMC convenes to review the aggregate safety data to determine if enrollment will resume, and the appropriate dose level moving forward. Additionally, the investigators and the PRA Medical Monitor will meet regularly (via teleconference, see [section 7](#)) to assess safety on an ongoing basis.

Meetings will be held approximately 1 week after the last patient completes the DLT period. The DLT period is defined as the time from start of study therapy in Cycle 1 through the start of day 1 of Azacitidine during Cycle 2, or the time at which a patient discontinues treatment due to study treatment-related toxicity prior to receiving Day 1 Cycle 2 treatment. This will occur for each dose escalation cohort that has been initiated and on an ad hoc basis as needed based on emerging safety data.

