9.1.1 Phase 1 Portion – Open-Label Dose Evaluation

Cohorts of 6 dose-limiting toxicity (DLT)-evaluable subjects will be enrolled in an open-label fashion to receive vadastuximab talirine in combination with azacitidine in 28-day cycles, starting at 5 mcg/kg vadastuximab talirine. The DLT-evaluable population will include all Phase 1 subjects who have completed at least Cycle 1 of treatment (Cycle 1 of treatment is completed when the patient receives the first dose of azacitidine on Day 1 of Cycle 2) *or* discontinued study treatment because of AEs, or for a safety-related reason before having had the opportunity to receive the first dose of azacitidine on Day 1 of Cycle 2. In the Phase 1 Portion of the study, DLTs will be defined as posttreatment grade 4 neutropenia or grade 4 thrombocytopenia lasting >42 days from the start of therapy, in the absence of evidence of active MDS, or any grade 3 or higher non-hematologic toxicity that is clearly NOT resulting from underlying MDS or azacitidine, with the exception of:

- a. Grade 3 allergic reaction, fatigue, asthenia, anorexia, or constipation
- b. Grade 3 nausea, vomiting, or diarrhea not requiring tube feeding or total parenteral nutrition or hospitalization
- c. Febrile neutropenia (which resolves with appropriate treatment or marrow recovery), infection, bleeding, or other expected direct complications of cytopenias due to active MDS

If 2 or more subjects in a 6-subject cohort have DLTs, that dose level will be considered to have exceeded the MTD. If 5 mcg/kg vadastuximab talirine in combination with azacitidine is considered tolerable (≤ 1 of 6 subjects experiences a DLT), a cohort of 6 DLT-evaluable subjects will receive 10 mcg/kg vadastuximab talirine and azacitidine. If 10 mcg/kg vadastuximab talirine in combination with azacitidine is considered tolerable, a cohort of 6 DLT-evaluable subjects will receive 15 mcg/kg, and if 15 mcg/kg vadastuximab talirine in combination with azacitidine is considered tolerable, a cohort of 6 DLT-evaluable subjects will receive 20 mcg/kg. If 5 mcg/kg vadastuximab talirine in combination with azacitidine is not considered tolerable (> 1 of 6 subjects experiences a DLT), a cohort of 6 DLT-evaluable subjects will receive 3 mcg/kg vadastuximab talirine and azacitidine. The dose-escalation plan is presented in [Figure 1](#).

Figure 1: Study Schematic – Phase 1 Portion

DLT = dose-limiting toxicity; MTD = maximum tolerated dose.

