 - Whole blood (MDSC and CD33 expression; [Section 11.4](#))
 - 192 hours (± 4 hours) after the end of the vadastuximab talirine infusion (Day 10 or 12)
- Day 28 (± 7 days):
 - Bone marrow biopsy to assess bone marrow cellularity. Cycle 1 marrow biopsy may be omitted if either a) patient has recovered counts to less than grade 3 cytopenias, ie, absolute neutrophil count (ANC) $>1000/\text{mcL}$ AND platelet count $>50,000/\text{mcL}$, without transfusion support, by Day 28 of Cycle 1 or b) there is evidence in the peripheral blood of active MDS, eg, circulating blasts.

Note:

- A. If the marrow is not hypocellular (total marrow cellularity $\geq 10\%$), the patient may proceed to Cycle 2 per dose modification guidance, depending on marrow blast percentage / remission status.*
- B. If the marrow is hypocellular (total marrow cellularity $< 10\%$), Cycle 2 should be delayed until count recovery (defined in Cycle 1 as thrombocytopenia and neutropenia improving to less than CTCAE grade 4, or by the following formula: $[(\text{NADIR COUNT}) + (\text{BASELINE COUNT} - \text{NADIR COUNT}) \times 0.75]$. If neutrophil count or platelet count have not recovered to less than Grade 4 by Day 42, a repeat marrow should be performed within a week. If the marrow is hypocellular at Day 42, then the subject will have experienced a DLT (posttreatment grade 4 neutropenia or grade 4 thrombocytopenia lasting > 42 days from the start of therapy in the absence of evidence of active MDS); if marrow cellularity has recovered to $\geq 10\%$, and ongoing cytopenia(s) are attributed to active MDS, then Cycle 2 may be initiated.*

10.2.1.2 Cycle 2

- Day 1 (± 1 day), pretreatment:
 - Biomarker assessments (Section 11.4)
 - Whole blood (sCD33 - cytokines and research; MDSC; CD33 expression; and PBMCs)
 - ECOG performance status and weight (Section 11.5)
 - PRO questionnaire (Section 11.9)
 - Clinical laboratory tests (CBC with differential, serum chemistry including ferritin, and urinalysis; Section 11.7)
 - Blood samples for ATAs (within 24 hours before beginning the azacitidine infusion; Section 11.8)
- Days 1 to 6 (if azacitidine is administered on 7 consecutive days) or Days 1 to 5, and 8 (if administered 5 days on/2 days off/2 days on): Administer azacitidine according to the selected treatment schedule (Section 9.5.1.3)
- Day 7 (if azacitidine is administered on 7 consecutive days) or Day 9 (if administered 5 days on/2 days off/2 days on), pretreatment:

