13.2 Sample Size Estimation

Phase 1 Portion (minimum of 6 subjects per cohort): Six subjects are adequate to appropriately assess the safety profiles and DLT rates of differing dose levels of vadastuximab talirine in combination with azacitidine. If the true incidence rate of DLT is 10%, the probability of considering a dose level tolerable (ie, ≤ 1 of 6 subjects experiences a DLT) will be 88.6%. If the true incidence rate of DLT is 50%, the probability of considering a dose level tolerable will be 10.9%.

Phase 2 Portion (106 subjects): A sample size of 106 subjects will provide 85% power to detect a treatment difference in ORR, assuming an ORR of 30% for azacitidine alone vs 55% for the combination of vadastuximab talirine with azacitidine, at a 2-sided 0.1 alpha level.

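### The SAP's DLT period can close, and the safety committee can meet, before the protocol's >42-day hematologic DLT is assessable in some Phase 1 subjects

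*SAP*

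**What the plan says.** The hematologic DLT in protocol 9.1.1, repeated in SAP 3.1.1, is grade 4 neutropenia or thrombocytopenia "lasting >42 days from the start of therapy, in the absence of evidence of active MDS". Two or more DLTs among six subjects put the dose above the MTD.

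SAP 7.1 runs the DLT period from the start of therapy "through the start of day 1 of Azacitidine during Cycle 2", or to an earlier discontinuation for treatment-related toxicity. It adds: "Meetings will be held approximately 1 week after the last patient completes the DLT period". The evaluation gates escalation: "Each dose cohort will be evaluated for DLTs prior to enrolling the subsequent cohort". Subjects receive "vadastuximab talirine in combination with azacitidine in 28-day cycles", so an undelayed Cycle 2 starts on Day 29.

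The start of Cycle 2 depends on the marrow rules in protocol 10.2.1.1 and on Tables 2 and 3:

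- **Note A (cellularity 10% or more):** "the patient may proceed to Cycle 2 per dose modification guidance", according to blast percentage or remission status.
- **Note B (cellularity below 10%):** "Cycle 2 should be delayed until count recovery". Recovery means either counts better than grade 4 or a formula based on nadir and baseline. If counts are still grade 4 at Day 42, the marrow is repeated within a week, and a hypocellular marrow is then a DLT.
- **Table 2, blasts below 5%:** a delay of up to 14 days is permitted but not required. Without recovery by Day 42, vadastuximab talirine is omitted and the next azacitidine follows Table 3.
- **Table 2, blasts 5% or more:** treatment may continue unmodified.

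Under protocol 13.5.3 a subject is DLT-evaluable once Cycle 2 azacitidine has been given. SAP 5.0 and 6.3 add any subject who had a DLT.

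**The concern.** The definition of the DLT and the period for observing it are not tied together. The definition needs more than 42 days. The period ends at an event that can fall near Day 29. Nothing in either document requires a subject with unresolved grade 4 counts to be followed to the end of the 42 days before the SMC evaluates the cohort.

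A subject who enters Cycle 2 in that state is DLT-evaluable and can be counted as DLT-free. Later counts fall outside the SAP's DLT period and are confounded by Cycle 2 treatment. Because the decision turns on one DLT versus two, a single unseen event can change whether the next cohort opens. The operating characteristics in protocol 13.2 describe the rule only if all DLTs are ascertained.

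**Working it through.** **1. The plan's own figures.** With X ~ Bin(6, p), the chance of calling a dose tolerable is P(X ≤ 1) = (1−p)^6 + 6p(1−p)^5.

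- p = 0.10: 0.8857, against a stated 88.6%.
- p = 0.50: 0.1094, against a stated 10.9%.

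Both reproduce.

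**2. Timeline.** Inputs: 28-day cycles and the 42-day criterion (protocol 9.1.1), the ±1 day window for Cycle 2 Day 1 (protocol 10.2.1.2), and the one-week interval to the meeting (SAP 7.1). Counting the start of therapy as Day 1, the criterion is first met on Day 43.

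| Cycle 2 Day 1 of last subject | SMC meeting (+7) | Relative to Day 43 |
|---|---|---|
| Day 28 | about Day 35 | 8 days before |
| Day 29 | about Day 36 | 7 days before |
| Day 30 | about Day 37 | 6 days before |
| Day 42 | about Day 49 | 6 days after |
| Day 43 | about Day 50 | 7 days after |

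The gap exists when Cycle 2 starts on time and disappears when Cycle 2 is held to Day 42.

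**3. Who can have an early close with grade 4 counts and no active MDS?**

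- *Cellularity 10% or more, blasts below 5%.* Note A refers to the dose-modification guidance, where the delay is optional. The DLT definition has no cellularity condition, so this subject can still be heading for a DLT.
- *A recovery formula met while still grade 4.* Grade 4 means ANC below 500/mm³ or platelets below 25 × 10⁹/L (SAP Appendix 3). The Note B formula is nadir + 0.75 × (baseline − nadir). With baseline ANC 600 and nadir 0 it is met at 0.75 × 600 = 450, still grade 4. With nadir 0 this can happen for baseline ANC below 500/0.75 ≈ 667 or platelets below 25/0.75 ≈ 33. Under the 0.50 formula in Table 2 the limits are 500/0.50 = 1000 and 25/0.50 = 50. Protocol 9.4.1 sets no minimum ANC or platelet count, so such baselines can enrol.
- *Discontinuation for treatment-related toxicity before Cycle 2.* SAP 7.1 closes the period at that point.

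**4. Illustration under assumption.** Let a share m of DLTs be unseen in k of the six subjects, with q = p(1−m). Then

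P(tolerable) = (1−p)^(6−k)(1−q)^k + (6−k)p(1−p)^(5−k)(1−q)^k + (1−p)^(6−k)·k·q(1−q)^(k−1).

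For example, with p = 0.5, k = 2 and m = 0.5, q = 0.25 and the terms are 0.0352 + 0.1406 + 0.0234 = 0.199.

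| p = 0.5 | m = 0 | m = 25% | m = 50% |
|---|---|---|---|
| last subject only (k = 1) | 10.9% | 12.9% | 14.8% |
| last two subjects (k = 2) | 10.9% | 15.1% | 19.9% |
| all six | 10.9% | 27.4% | 53.4% |

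The values of m and k are assumptions. The documents do not split DLTs into hematologic and non-hematologic, or early and late.

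**The case against.** The strongest reply is that the DLT period is event-driven and does not end at a fixed Day 29. Note B holds Cycle 2 for a hypocellular marrow and makes the DLT call at Day 42, so the period stays open and the SMC meets at about Day 49 or later. Tables 2 and 3 anticipate a similar wait when blasts are below 5% and counts have not recovered. Blasts of 5% or more point to active MDS, which the DLT definition excludes. A subject who is better than grade 4 at Cycle 2 Day 1 cannot have the >42-day event from that episode. All of this stands. A reader might infer that the hematologic DLT can never be observed before the SMC meets; these provisions rule that reading out.

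It can also be said that late events are not lost. SAP 5.0 and 6.3 keep any subject who had a DLT, a CBC is scheduled on Day 15 of Cycle 2 (about Day 43 if on time), the SMC can meet ad hoc, and subjects enrolled earlier will usually have passed Day 42 by the meeting. This answers the inference that late DLTs are structurally excluded from the final tables. It does not close the gap in the cohort decision. Neither document says that a DLT after the period has closed counts for escalation, or that the SMC waits for it, and ad hoc meetings are discretionary. The point about earlier subjects concerns meeting timing only: the period is defined per subject, so it closes early for them too.

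**Conclusion.** The point holds in limited form. The SAP's DLT period and the protocol's hematologic DLT definition are not aligned, and for the three residual routes the period can close, with the SMC meeting 6 to 8 days too early after an on-time Cycle 2. The main hypocellular pathway is covered.

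The figures of 88.6% and 10.9% are not in error; they are conditional on full ascertainment. The actual effect on them cannot be derived from the documents. If 25% to 50% of DLTs went unseen in only the last one or two subjects, a dose with a true 50% DLT rate would be called tolerable about 13% to 20% of the time, against 10.9%. A reader might take 27% to 53% as the real error rate. That is an upper scenario, requiring the same share to be missed in all six subjects, and the documents do not support it. The matter is still worth correcting, since one event decides escalation.

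**What to change.** Reconcile the DLT period in SAP 7.1, and the matching text in SAP 5.0 and 6.3 and protocol 13.5.3, with the >42-day definition. For any subject with grade 4 neutropenia or thrombocytopenia unresolved at Cycle 2 Day 1 or at discontinuation, keep DLT status open until resolution or the end of the 42-day window. Make the SMC cohort evaluation once all six statuses are closed. State how active MDS will be judged for a subject who is already in Cycle 2.

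No dose or treatment rule needs to change for this. Separately, the sponsor should reconcile the Cycle 2 start rules in protocol 10.2.1.1 with Table 2. They use different recovery formulas (0.75 and 0.50). They also treat low cellularity differently: delay below 10% in Note B, against permanent discontinuation of vadastuximab talirine or blinded treatment at 10% or less in Table 2 footnote a.

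The cost is wording, plus a wait before some SMC decisions. That wait is about one week (Day 36 to Day 43), or up to about two if a repeat marrow, allowed until about Day 49, is awaited.
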